APPENDIX 4. MANAGEMENT OF SKIN TOXICITIES

Cutaneous adverse events have been observed in subjects receiving MEK inhibitors (ie, trametinib [Mekinist USPI] and cobimetinib [Cotellic USPI]) and ERK inhibitors (ulixertinib and GDC-0994) (de la Cruz-Merino et al 2017; Sullivan et al 2018; Li et al presentation 2017, Varga et al 2020; Infante et al abstract 2015; Infante et al presentation 2015; Macdonald et al 2015; Reyes-Habito et al 2014; Anforth et al 2013; Mandalà et al 2013; Manousaridis et al 2013).

Suggested guidelines regarding management and criteria for adjusting, withholding, and discontinuing study treatment for skin toxicities considered to be related to study treatment are provided in Table 15. The institutional standards for the management of skin-related AEs can differ from these guidelines. In this case, best clinical judgment should be applied.

CTCAE		
Grade	Management	Action and Dose Modification
Grade 1	 Initiate symptomatic measures. Use moderate strength topical steroid.^a Consider topical antibiotics or combined topical steroids/antibiotics if acneiform papulopustular rash. Consider oral antibiotics. Consider oral antihistamines if maculopapular rash. Reassess after 1 week. 	 Continue study treatment and monitor for change in severity. If no recovery to ≤Grade 1 within 2 weeks despite best supportive care, reduce study treatment by 1 dose level.^b
Grade 2	 Initiate symptomatic measures. Use moderate strength topical steroid.^a Obtain bacterial/viral/fungal cultures if infection is suspected. Initiate topical antibiotics and, if rash is persistently ≥Grade 2 after 1 week, initiate oral antibiotics for 6 weeks (doxycycline 100 mg BID or minocycline 100 mg BID) if acneiform papulopustular rash. Initiation of oral antibiotics at first sign of Grade 2 acneiform papulopustular rash is also appropriate. Initiate oral antihistamines or oral steroid^c if maculopapular rash. Consider dermatology referral for evaluation and biopsy. Reassess after 1 week. 	 Reduce study treatment by 1 dose level. After reduction, if recovery to ≤Grade 1, increase dose to previous dose level. After reduction, if no recovery to ≤Grade 1 within 1 week, interrupt study treatment until recovery to ≤Grade 1 and restart with study treatment reduced by 1 dose level.^d
Grade ≥3	 Initiate symptomatic measures. Use moderate strength topical steroid^a plus oral steroids. Obtain bacterial/viral/fungal cultures if infection is suspected. Initiate oral antibiotics (doxycycline 100 mg BID or minocycline 100 mg BID or oxytetracycline 500 mg BID) if acneiform (papulopustular) rash. Initiate oral antihistamines if maculopapular rash. Consider dermatology referral for evaluation and biopsy. Reassess after 1 week. 	 Interrupt study treatment until recovery to ≤Grade 1.^d Restart with study treatment reduced by 1 dose level.^b If no recovery to ≤Grade 1 within 3 weeks, permanently discontinue study treatment.

Table 15: Suggested Management and Dose Modification Guidelines for Skin Toxicities

BID=twice a day; CTCAE=Common Terminology Criteria for Adverse Events.

^a Hydrocortisone 2.5% cream or fluticasone 0.5% cream.

^b Escalation to previous dose level may be considered if no skin toxicity is evident for 4 weeks after restarting study treatment.

^c Prednisolone 0.5 mg/kg/day or equivalent (up to 60 mg/kg/day) for 5 to 7 days.

^d Approval of the Sponsor's medical monitor is required to restart study treatment after interruption ≥ 21 days.

Preventative care measures for skin toxicities should include:

- Avoid sun exposure.
- Apply broad spectrum sunscreen twice daily (SPF >15).
- Use thick, alcohol-free emollient cream on dry areas at least twice daily.

Symptomatic care should include:

- Pruritic lesions: cool compresses and oral antihistamine.
- Paronychia: antiseptic bath, oral antibiotic, and local corticosteroids.
- Fissuring lesions: silver nitrate or zinc oxide cream.
- Desquamation: emollients and mild soap.

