7.1.7. Transition From Fed to Fasted Administration

At the time of Amendment 2.0, dose escalation (Phase 1 Part A) was ongoing. In Phase 1 Part A, ASXT029-01 dose was escalated in sequential cohorts from 10 mg/day to 200 mg/day QD using the PiB form in fed subjects. One DLT (Grade 3 nonserious maculo-papular rash) was reported in the 200-mg/day PiB cohort. Six subjects were enrolled in the tablet-bridging cohort at 80 mg/day QD under fed conditions with no DLTs being reported, and enrollment was ongoing in the 120-mg/day QD tablet cohort.

Preliminary PK data at the time of Amendment 2.0, showed relatively high variability for systemic exposures after ASTX029 was dosed with food. The geometric mean (CV%) plasma AUC_{0-inf} values on C1D1 were 2377(170) ng•h/mL for the 80-mg tablet-bridging cohort (n=4), compared with 4053(83) ng•h/mL for the 120 mg PiB (n=5) cohort and 8304(53) ng•h/mL for the 200 mg PiB cohort (n=9).

With Protocol Amendment 2.0, administration under fasted conditions was introduced. Fasted administration may result in higher exposure of ASTX029 at lower doses (Section 1.3.2.1) and potentially reduce intersubject variability compared with administration with food.

Transition to fasted-state dosing occurred during Phase 1 Part A by dosing a bridging cohort of 3 subjects at a dose of 40 mg/day tablets QD. Starting with Amendment 3.0, dose escalation under fed conditions was discontinued, and dose escalation under fasted conditions is ongoing. Please refer to the current ASTX029 IB for preliminary PK and safety data.

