7.5. Guidelines for Adjusting, Withholding, or Discontinuing Study Treatment

ASTX029 dosing should be withheld in the case of a DLT in Cycle 1 or toxicity in subsequent cycles that would have qualified as a DLT if it had occurred in Cycle 1. Dosing may resume, at the investigator's discretion, if and when study-treatment-related toxicity has:

- Completely resolved or
- Returned to baseline or partially recovered to ≤Grade 2 (anemia, fatigue, malaise, and alopecia) or returned to baseline or partially recovered to ≤Grade 1 (all other toxicities).

If and when a decision is made to resume dosing, the individual's dose should be adjusted to the previously assessed lower dose level that was considered safe by the DSRC. A maximum of 2 dose reductions are permitted for any single subject. In the event of further unacceptable toxicity, the investigator should consider discontinuation of study treatment for that subject.

If toxicity has not resolved as described above within 21 days, the investigator should permanently discontinue study treatment unless the subject is receiving compelling benefit, the

benefit of the study treatment exceeds the risks, and no alternative therapy is available. Approval by the Sponsor's medical monitor is required to restart study treatment after an interruption \geq 21 days, and study treatment must be administered at a dose approved by the Sponsor's medical monitor when toxicity has resolved as described above.

Suggested guidelines and criteria for adjusting, withholding, or discontinuing study treatment as a result of skin toxicities, ocular toxicities, diarrhea, liver toxicities, and LVEF decrease are provided in Appendix 4, Appendix 5, Appendix 6, Appendix 7, and Appendix 8, respectively. The institutional standards for the management of these toxicities can differ from the suggested guidelines. In this case, best clinical judgment should be applied.

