14.4. Study Administrative Letters and Protocol Amendments

The Sponsor may issue Study Administrative Letters (1) to clarify certain statements or correct obvious errors/typos/inconsistencies in the study protocol, (2) to change the logistical or administrative aspects of the study, such as study personnel or contact information, or (3) to instruct investigators of DSRC safety decisions for immediate implementation for safety reasons (Section 4.4).

For all other changes, the Sponsor will initiate any change to the protocol in a protocol amendment document. The study center will submit the amendment to the IRB/IEC together with, if applicable, a revised model ICF. If the change in any way increases the risk to the subject, information on the increased risk must be provided to subjects already actively participating in the study, and they must read, understand, and sign any revised ICF confirming willingness to remain in the study.

The investigator must obtain IRB/IEC approval before any protocol amendment can be implemented, except for administrative changes or changes necessary to eliminate an immediate risk to study subjects, as outlined above.

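### Protocol Table 15 footnote c sets the oral steroid dose and its upper limit in the same per-kilogram unit, so the limit is 120 times the dose at any body weight

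*Protocol*

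**What the plan says.** Protocol Appendix 4, Table 15, lists supportive care and study-drug modifications for skin toxicity by CTCAE grade.

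- **Grade 2 row, management column:** "Initiate oral antihistamines or oral steroid^c if maculopapular rash". The superscript leads to footnote c.
- **Footnote c:** "Prednisolone 0.5 mg/kg/day or equivalent (up to 60 mg/kg/day) for 5 to 7 days".
- **Grade ≥3 row:** it also calls for oral steroids, but in the text available it carries no dose and no marker for footnote c.
- **Status of the table:** Appendix 4 calls it suggested guidance and adds that "The institutional standards for the management of skin-related AEs can differ from these guidelines". Section 7.5 says the same of all the toxicity tables: "The institutional standards for the management of these toxicities can differ from the suggested guidelines".
- **Grade 1 row, dose-modification column:** "Continue study treatment and monitor for change in severity", followed by "If no recovery to ≤Grade 1 within 2 weeks despite best supportive care, reduce study treatment by 1 dose level".

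**The concern.** An upper limit is useful only if it can restrain the dose beside it. In footnote c the dose and the limit are in the same per-kilogram unit and are two orders of magnitude apart. The limit therefore either does nothing or permits a very large multiple of the stated dose, and a reader cannot tell which was intended.

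What is at stake is patient safety and consistent instructions to sites. Rash is an expected effect of this drug class (Section 8), and maculo-papular rash has occurred in the study. Section 7.1.7 records that "One DLT (Grade 3 nonserious maculo-papular rash) was reported in the 200-mg/day PiB cohort". Supportive care also bears on a study decision: under Section 7.4, a symptomatic Grade 2 skin toxicity is dose-limiting only if it fails to improve within 7 days despite supportive treatment and stopping study drug. That link is secondary to the safety point.

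A smaller matter sits in the same table. As the Grade 1 row reads, its two-week trigger for reducing study drug cannot be met by an event that stays at Grade 1, because such an event is already at Grade 1 or below.

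**Working it through.** The plan states no ratio or daily maximum on this point, so there is no figure of its own to reproduce. All inputs come from footnote c.

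**Inputs**
- Stated dose: 0.5 mg/kg/day
- Bracketed upper limit: 60 mg/kg/day
- Duration: 5 to 7 days

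**Step 1: ratio of limit to dose.** For a subject weighing W kg, the daily dose is 0.5 × W mg and the daily limit is 60 × W mg. The ratio is (60 × W) / (0.5 × W) = 60 / 0.5 = 120. W cancels, so no body weight has to be assumed.

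**Step 2: course totals per kilogram.**

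| | 5 days | 7 days |
|---|---|---|
| Stated dose | 0.5 × 5 = 2.5 mg/kg | 0.5 × 7 = 3.5 mg/kg |
| Bracketed limit | 60 × 5 = 300 mg/kg | 60 × 7 = 420 mg/kg |

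Check: 300 / 2.5 = 120 and 420 / 3.5 = 120. The second row of the table applies only if the bracket is read as a permitted range.

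**Step 3: possible readings.**
- *Cap on the stated dose.* 0.5 is below 60 at every weight, so the cap never binds.
- *Permitted range.* Doses up to 120 times the stated one are allowed.
- *Limit on the equivalent agent only.* The bracket follows the allowance for an equivalent drug. A dose equivalent to 0.5 mg/kg/day of prednisolone is no better explained by this limit, so this reading does not rescue the footnote.

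**Step 4: does anything else settle it?** The Grade ≥3 row gives no oral steroid dose. Footnote a covers topical creams only. Appendix 6 names a steroid among second-line options for diarrhea but gives no dose. The SAP does not address the matter.

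**Step 5: the Grade 1 row.** An event that stays at Grade 1 always satisfies the recovery condition, so it cannot trigger a reduction. An event that worsens to Grade 2 and does not come back within two weeks would meet the wording. However, the Grade 2 row already calls for a reduction by 1 dose level, with no two-week wait. The two rows overlap with different timing.

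**The case against.** The strongest reply has four parts.

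1. *The figures are not strictly incompatible.* A dose of 0.5 mg/kg/day does lie below 60 mg/kg/day, so this could be called an ineffective limit, not a contradiction. That is fair as a matter of logic. It does not help a site, because a limit that cannot limit anything, or that allows 120 times the dose, needs correcting under either name.

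2. *The table is advisory.* Institutional standards may differ, best clinical judgment applies, and the starting dose itself is clear. This stands and is why the point is not rated higher. A site with no differing standard still has this figure in front of it.

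3. *The reported rash is weak support.* It was Grade 3, whereas footnote c is called from the Grade 2 row. It also occurred with the powder-in-bottle form, which has been phased out; Section 7.1.6 says all subjects who received it had stopped study drug by Amendment 4.0. This stands. The event shows that this kind of rash occurs with the drug, not that footnote c was used.

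4. *The Grade 1 wording is a separate matter and depends on a comparison sign that may not have survived conversion of the PDF.* This also stands. The Grade 1 remark is minor, holds only for the text as it reads here, and carries none of the rating.

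**Conclusion.** The point holds: footnote c is wrong as written. The bracketed limit is exactly 120 times the stated dose at every body weight. It either has no effect or permits 120 times the stated dose, and nothing else in the two documents resolves the ambiguity. The result uses only the footnote's two figures. It does not depend on why the per-kilogram unit appears on the limit, which the documents do not show.

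This should be fixed because it is a dosing figure in current text and is cheap to correct. The rating rests on footnote c alone. No sample size, error rate or efficacy analysis changes.

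**What to change.** The sponsor's medical team should reconcile the dose, the limit and the unit of the limit in footnote c. No dose, limit or unit is suggested here. Section 14.4 allows an administrative letter "to clarify certain statements or correct obvious errors/typos/inconsistencies in the study protocol", and the footnote correction could go out that way or with the next amendment.

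The Grade 1 trigger and the Grade 2 row should be reconciled at the same time. If that changes when study drug is reduced, and does more than clarify wording, Section 14.4 points to an amendment for that part.

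The cost is one corrected footnote and clarified wording in the Grade 1 and Grade 2 rows. No data collection or analysis changes.

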APPENDIX 5. MANAGEMENT OF VISUAL CHANGES

Ocular adverse events have been observed in subjects receiving MEK inhibitors (ie, trametinib [Mekinist USPI] and cobimetinib [Cotellic USPI]) and ERK inhibitors (ulixertinib and GDC-0994 [de la Cruz-Merino et al 2017; Sullivan et al 2018; Li et al presentation 2017; Maubon et al 2016; Stjepanovic et al 2016; Varga et al 2020; Duncan et al 2015; Infante et al abstract 2015; Infante et al presentation 2015; Welsh and Corrie 2015; Ho et al 2013]). Ocular toxicities include blurring and altered light perception, periorbital edema, increased lacrimation, uveitis, and visual disturbances. Retinal adverse events have also been described in subjects receiving MEK inhibitors (de la Cruz-Merino et al 2017; Stjepanovic et al 2016; Welsh and Corrie 2015).

The causal relationship between a change in vision and the study treatment should be carefully explored, and an ophthalmologist should be consulted. Special attention should be given to retinal adverse events (eg, CSR, RVO). For events of visual changes regardless of severity, a blood sample for PK analysis must be drawn as close as possible to the time of the event.

Suggested guidelines regarding management and criteria for adjusting, withholding, and discontinuing study treatment for visual changes considered to be related to study treatment are provided in Table 16. The institutional standards for the management of ocular AEs can differ from these guidelines. In this case, best clinical judgment should be applied.

CTCAE Grade	Management	Action and Dose Modification
Grade 1	Consult ophthalmologist within 7 days of onset	 Continue study treatment. If dilated fundus examination cannot be performed within 7 days of onset, interrupt study drug. If RVO or CSR excluded, continue study treatment at the same dose level. If CSR suspected or diagnosed, continue study treatment at the same dose level. If RVO diagnosed, permanently discontinue study treatment and report as an SAE.
Grade 2	Interrupt study treatment and consult ophthalmologist immediately	 If RVO or CSR excluded, resume study treatment at the same dose level. If CSR diagnosed, withhold study treatment. If improved to ≤Grade 1, resume at a lower dose level^a with close monitoring following treatment re-initiation. If RVO diagnosed, permanently discontinue study treatment and report as an SAE.
Grade 3	Interrupt study treatment and consult ophthalmologist immediately	 If RVO or CSR excluded, withhold study treatment. If improved to ≤Grade 1, resume at a lower dose level. If CSR diagnosed, withhold study treatment. If improved to ≤Grade 1, resume at a lower dose level^a with close monitoring following treatment re-initiation. If RVO diagnosed, permanently discontinue study treatment and report as an SAE.
Grade 4	Interrupt study treatment and consult ophthalmologist immediately	Permanently discontinue study treatment and report as an SAE.

 Table 16:
 Suggested Management and Dose Modification for Visual Changes

CSR=central serous retinopathy; CTCAE=Common Terminology Criteria for Adverse Events; RVO=retinal vein occlusion; SAE=serious adverse event.

^a Dose level depends on the nature of the ocular toxicity. Approval of the Sponsor's medical monitor is required to restart study treatment after interruption ≥ 21 days.

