APPENDIX 6. MANAGEMENT OF DIARRHEA

Episodes of diarrhea have occurred in subjects receiving MEK inhibitors (ie, trametinib [Mekinist USPI] and cobimetinib [Cotellic USPI]) and ERK inhibitors (ulixertinib and GDC-0994) (Adjei et al, 2017; Sullivan et al 2018; Li et al presentation 2017; Varga et al 2020; Infante et al abstract 2015; Infante et al presentation 2015; Welsh and Corrie 2015).

Suggested guidelines regarding management and criteria for adjusting, withholding, and discontinuing study treatment for diarrhea considered to be related to study treatment are provided in Table 17. The institutional standards for the management of GI AEs can differ from these guidelines. In this case, best clinical judgment should be applied.

CTCAE Grade	Management	Action and Dose Modification
Uncomplicated ^a Grade 1 or 2	 Diet: stop lactose-containing products; BRAT diet recommended. Hydration: 8 to 10 large glasses per day. Loperamide^b: Initially 4 mg followed by 2 mg every four hours; maximum 16 mg/day. Continue until diarrhea-free for 12 hours. Diarrhea >24 hours: loperamide every 2 hours, maximum 16 mg/day. Consider adding oral antibiotics. Diarrhea >48 hours: loperamide every 2 hours; maximum 16 mg/day. Consider second-line therapies (budesonide, tincture of opium, or octreotide) and oral antibiotics. Rule out other causes (eg, infection). 	 Continue study treatment. If diarrhea is Grade 2 for >48 hours, interrupt study treatment until diarrhea resolves to ≤Grade 1.° Resume study treatment at the same dose level.
Uncomplicated ^a Grade 3	 Diet: stop lactose-containing products; BRAT diet recommended. Hydration: 8 to 10 large glasses per day. Loperamide^b: Initially 4 mg followed by 2 mg every four hours; maximum 16 mg/day. Continue until diarrhea-free for 12 hours. Second-line therapies and antibiotics if clinically indicated. Hydration: IV fluids if clinically indicated. Rule out other causes (eg, infection). 	 Inform the Sponsor's medical monitor Interrupt study treatment until diarrhea resolves to ≤G1.^c Resume with study treatment at a lower dose level.^c
Grade 4 Any complicated ^d diarrhea	 Urgent intervention indicated. Intervention may require hospitalization for subjects at risk of life-threatening complications. 	 Inform the Sponsor's medical monitor. Permanently discontinue study treatment and report as an SAE.

 Table 17:
 Suggested Management and Dose Modification for Diarrhea

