APPENDIX 8. DOSE MODIFICATION FOR DECREASE IN LEFT VENTRICULAR EJECTION FRACTION

Decreases of LVEF have been observed in patients receiving the MEK inhibitors trametinib (Mekinist USPI) and cobimetinib (Cotellic USPI) and the ERK inhibitor GDC-0994 (Varga et al 2020). ECHO or MUGA scans will be performed to assess cardiac ejection fraction in regular intervals as outlined in the schedule of events tables (Table 11 and Table 12).

Suggested guidelines regarding management and criteria for adjusting, withholding, and discontinuing study treatment for LVEF decrease are provided in Table 18. In the event that institutional standard practice differs from these suggested guidelines, institutional practices may be followed with best clinical judgement applied.

LVEF Decrease (%)	Action and Dose Modification	
Resting LVEF 49% to 40%; absolute decrease of >10% but <19% in LVEF from baseline and LVEF below the institution's LLN	 Interrupt study treatment and perform ECHO within 3 weeks. If ECHO recovers within 3 weeks: Consult with the Sponsor's medical monitor and request approval to restart ASTX029 dosing. If approval is obtained, restart at a lower dose level. If ASTX029 is restarted, repeat ECHO after 3, 6, and 9 weeks after restart; continue in intervals of every 12 weeks thereafter. If ECHO does not recover within 3 weeks: Consider cardiology consultation. Permanently discontinue study treatment. Repeat ECHO after 3, 6, and 9 weeks or until resolution or 	
Resting LVEF 39% to 20% or >20% absolute reduction from baseline	 plateau. Inform the Sponsor's medical monitor. Permanently discontinue study treatment. 	
Resting LVEF <20%	Consult with a cardiologist.Repeat ECHO after 3, 6, and 9 weeks or until resolution.	

 Table 18:
 Suggested Action and Dose Modification for LVEF Decrease

ECHO=echocardiogram; LVEF=left ventricular ejection fraction; LLN=lower limit of normal.

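### Table 16's Grade 2 line for eye events resumes the same dose with no limit for persistent toxicity, and conflicts with Section 7.5 once an event has stayed Grade 2 for more than 7 days off drug

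*Protocol*

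**What the plan says.** Three parts of the protocol bear on the same event.

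- **Appendix 5, Table 16, Grade 2 row.** Treatment is interrupted and an ophthalmologist is consulted at once. The next step depends on the diagnosis. When retinal vein occlusion (RVO) and central serous retinopathy (CSR) are ruled out, the line reads "If RVO or CSR excluded, resume study treatment at the same dose level". In the Grade 3 row the matching line reads "If RVO or CSR excluded, withhold study treatment. If improved to ≤Grade 1, resume at a lower dose level".
- **Scope of Table 16.** The lead-in says that the guidelines on "study treatment for visual changes considered to be related to study treatment are provided in Table 16". The appendix names class effects that are neither RVO nor CSR: "Ocular toxicities include blurring and altered light perception, periorbital edema, increased lacrimation, uveitis, and visual disturbances".
- **Section 7.4.** An eye disorder of Grade 2 or worse is a dose-limiting toxicity (DLT) if it has not improved to Grade 1 or less within 7 days although drug was stopped. Documented RVO also counts. Events with a clear alternative cause are excepted.
- **Section 7.5.** Dosing should be withheld for a DLT in Cycle 1, and for a later toxicity that would have been one. It may resume once the related toxicity has resolved, returned to baseline or, for eye events, reached Grade 1 or less. The restart dose should be a lower level that the DSRC has already judged safe. At most 2 reductions are allowed per subject. If recovery has not come within 21 days, treatment should stop for good unless a stated benefit exception applies.

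Section 7.5 also sends the investigator to Appendix 5 for ocular toxicity and describes the appendix tables as suggested guidelines.

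**The concern.** An investigator with a Grade 2 eye event that is slow to clear will find two answers in the protocol. Table 16 is the more specific text and the one written for ocular events. Its line turns only on the diagnosis and has no branch for an event that has not improved. Section 7.5 turns on grade and duration.

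At stake is the restart dose and its timing after a drug-related eye toxicity. Section 7.3 has already fixed the Phase 2 dose at 200 mg daily, so the line acts as default guidance for Phase 2 subjects and for those who carry on in the extension (Section 5.4.5). Two sites could treat the same event differently and both cite the protocol.

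**Working it through.** No sample size, power or error rate enters here, so the check is to take one case through the texts.

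**Case.** A subject on 200 mg has an eye event judged related to study drug. It is Grade 2, drug is stopped, and RVO and CSR are ruled out.

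**Step 1: is it a DLT or the later-cycle equivalent?** Section 7.4 does not need RVO or CSR to be present; persistence at Grade 2 is enough. The alternative-cause exception does not remove the case, because Table 16 deals with related events. The answer therefore turns on *d*, the number of days off drug with the event still at Grade 2.

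**Step 2: compare the instructions by *d*.**

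| *d* | Section 7.5 | Table 16, Grade 2, RVO/CSR excluded | Conflict |
|---|---|---|---|
| 7 or less | not triggered | same dose; 0 of 2 reductions used | none |
| more than 7, up to 21 | should withhold (0 mg) until resolved, baseline or Grade 1 or less; then a lower level; 1 of 2 reductions used | same dose (200 mg) now; 0 of 2 reductions used | timing and dose |
| more than 21 | should stop permanently unless the exception applies | same dose | restart at all |

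On day 8 off drug, still at Grade 2, the same subject may have 200 mg under the table and should have 0 mg under Section 7.5.

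**Step 3: does other text settle it?**
- Section 7.1.4 refers to Section 7.5 for reducing, withholding or stopping drug, and Section 7.5 refers on to Appendix 5. Neither states an order of precedence.
- The footnote to Table 16 calls for medical monitor approval after an interruption of 21 days or more. It sets no grade condition and is attached to the CSR lines.
- The clinical-judgment wording in Section 7.5 and Appendix 5 covers institutional standards that differ from the tables. It does not cover a table that differs from Section 7.5.

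**What cannot be computed.** The documents do not give the fasted dose level directly below 200 mg, so the gap in mg or in dose intensity is not stated here. They also give no rate for persistent Grade 2 eye events.

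**The case against.** The best defense is that the texts can be read together: Section 7.5 is the rule in the body, Table 16 is a suggested supplement, and silence on recovery lets Section 7.5 supply the condition. The window is also narrow. The ophthalmologist is consulted at once, so a prompt exclusion of RVO and CSR would usually lead to restart before day 8. Section 7.5 says *should* throughout, and investigators may hold or reduce drug at any time. All of this stands, and it lowers the weight of the point. It does not remove it, because the reader must supply a hierarchy that the protocol does not state.

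A reader might go further and infer that the line is wrong at any duration, since it permits restart before recovery. A count seems to support this. Tables 15 to 18 hold 2 + 4 + 2 + 1 = 9 lines that restart drug after an interruption, and 2 + 3 + 2 + 1 = 8 of them wait for recovery. Table 15 has "interrupt study treatment until recovery to ≤Grade 1 and restart with study treatment reduced by 1 dose level", Table 18 has "If ECHO recovers within 3 weeks", and Table 17 has "interrupt study treatment until diarrhea resolves to ≤Grade 1" followed by "Resume study treatment at the same dose level". The documents do not support that inference, for these reasons:

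- At 7 days or less Section 7.5 is not triggered, so nothing is breached.
- The Grade 2 interruption can be read as a diagnostic hold. The Grade 1 row has the same shape: stop if the fundus cannot be examined in time, and carry on at the same dose once RVO and CSR are excluded.
- The step from same dose at Grade 2 to hold-and-reduce at Grade 3 fits deliberate grading by severity.
- Dosing through Grade 2 toxicity is accepted elsewhere. Table 15 first reduces the dose without interrupting it, and Table 17 continues drug for up to 48 hours of Grade 2 diarrhea.

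The count shows that the line is unusual. It does not show that it is a mistake.

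**Conclusion.** The conflict is real but narrow. For a related eye event, with RVO and CSR excluded and still at Grade 2 after more than 7 days off drug, Table 16 and Section 7.5 (read with the ocular DLT definition in Section 7.4) give different instructions on when to restart and at what dose. Same-dose restart at 7 days or less is consistent with the protocol and may be intended.

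This rests on two assumptions. The first is that the 7 days run from the first day off drug; Section 7.4 names no starting point, and a count from onset would move the boundary when drug was stopped later. The second is that some work-ups or holds last beyond that boundary; the number of subjects is unknown.

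Severity is minor. A reader might infer that Phase 1 DLT calls or the recommended dose are in doubt. They are not: Section 7.4 defines DLTs without reference to Table 16, and Section 7.3 already records the 200 mg decision. The objective response rate analysis, sample size and error rates do not change. Nor do the documents show harm: the listed eye toxicities, uveitis among them, are cited as class observations with MEK and ERK inhibitors.

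**What to change.** Keep the line and add an exception at its end: *unless the event has not improved to Grade 1 or less (or baseline) within 7 days off treatment, in which case withhold and restart at a lower dose level per Section 7.5.*

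Whether recovery should also be required before a restart within the first 7 days is a clinical choice for the sponsor and the DSRC, and this point does not ask for it.

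The cost is one line of text and no new procedure. Because it changes dosing guidance, it should go out as a DSRC safety decision (Sections 4.4 and 14.4) or in the next amendment. The downside is a longer hold and a dose reduction for the few subjects whose Grade 2 event persists, which Section 7.5 already calls for.
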